7.1 CLINICAL CENTERS

The study will be conducted in up to 20 sites (with a maximum of 10 sites during the initial phase) in the United States and Europe. Each clinical center will be required to obtain IRB approval for the protocol and consent (and their revisions) in a timely fashion, to recruit patients, to collect data and enter it accurately in the electronic data capture (EDC) system, to faithfully follow the protocol and adhere to the standards of Good Clinical Practice (GCP). In addition, centers will be required to provide the DCC with the information necessary for interim, annual, and final reports, to provide source documents, data and regulatory documents for study monitors, provide prompt responses to DCC inquiries, and to participate in analyses and reporting of study results.

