10.6 POWER AND SAMPLE SIZE

Power for this study was determined based on the following operating characteristics: (a) two sided type I error fixed at 0.0492, assuming one interim analysis, (b) 85% power, (c) minimum follow-up of 18 months, (d) 18-months event rate in the ICD alone group of 19% (e) expected 18-month relative rate reduction in the ICD + RSDN group of $\geq 40\%$, accrual period of 48 months and non-uniform accrual.

Under the above assumptions it is estimated that 70 events (or 462 patients) will be required to detect a relative decrease in the relative event rate reduction requiring any ICD therapy $\geq 40\%$ in the ICD + RSDN compared to the ICD alone group (19% vs. 11.4%) (Lachin, 1981).

Lost to Follow Up: The term "lost to follow-up" is used to define an individual who has withdrawn consent to be in the study or who can no longer be located or assessed. Such individuals represent those for whom primary outcome assessment is no longer possible. Since the primary outcome will be assessed by interrogating the ICD and since patients come back to

the hospital for regular check we do not anticipate a high rate of lost to follow-up. The estimated sample size accounts for 5% attrition due to withdrawal of consent.

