10.8 STATISTICAL ANALYSIS

The primary analysis will be an intent-to-treat analysis that will include all randomized participants regardless of treatment actually received or follow-up schedule.

Point Estimation and Interval Estimation: We will report maximum likelihood estimates for point estimation. For routine reporting, two-sided 95% confidence intervals for all parameters will be prepared.

Disposition of Participants and Baseline Comparisons: Summaries of all participants randomized and the number who complete visits at 30-days, and every 6 months after the day of randomization will be provided for each treatment group. The treatment groups will be compared at baseline with respect to demographics, baseline measurements related to efficacy and baseline measurements related to safety.

Univariate Analysis: All outcome measures will be described in a univariate analysis. For continuous variables means and standard deviations will be calculated. For discrete and dichotomous variables we will use contingency tables.

Analysis of Primary Endpoint: The primary endpoint of this study is defined time to first event requiring any ICD therapy (appropriate or inappropriate) or Incessant VT (VT occurring below the ICD rate cut-off); this will be assessed in the on-treatment patient cohort. An event requiring ICD therapy is defined as an anti-tachycardia pacing (ATP) or shock therapy. Time to event will be estimated using Kaplan-Meier curves. Survival time will be defined as the time (in months) between randomization and the occurrence of first ICD therapy. To compare the ICD+ RSDN arm with the ICD alone arm we will use a stratified log-rank statistic (using the stratification variables from the randomization procedure). A Cox proportional hazards model with treatment and other important prognostic factors as covariates will be used for the multivariate analysis of the times to first ICD therapy. Risk ratios and their 95% confidence intervals will be computed. Patients will be included in the analysis as censored if they are alive and free of ICD events at the end of the 18-month follow-up period. Although we do not anticipate interactions between treatment and stratification factors, formal tests for interactions will be assessed using proportional hazards models. A formal test of proportional hazards will assess the significance of

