the interaction between the indicator for treatment group and log (t) in a Cox proportional hazards regression model that also includes the main effect for the randomization group. The final analysis will be based on a two tailed 0.0492 level test.

Analysis of Secondary End-points: All continuous variables will be analyzed using mixed effects models (Bagiella et al. 2000; Diggle et al. 1994; Laird and Ware 1982). Log-transformations will be used, if necessary to normalize the variables or stabilize the variance. For binary and discrete outcomes we will use generalized estimating equations (GEE) (Liang and Zeger 1986; Miller et al. 1993; Zeger and Liang 1986) to fit logistic or log-linear models that account for the dependency of the repeated measures.

Missing Data: For participants who withdraw consent to participate we will use all the information available up to the time of withdrawal. For the purpose of the primary analysis these patients will be censored at the time of withdrawal if they have not experienced the primary event. For all other variables, if the data are missing at random (MAR), that is, the probability of being missing depends only on observed values (Little and Rubin 1987), then likelihood-based methods such as mixed-effects models will be used for analysis without bias. If the fraction of missing data is small we expect that even non-ignorability can have only little effect on the final estimates. If the extent of missingness is large compared to the effect size, we will use the multiple imputation procedure proposed by Rubin (1997) and Little (1996).

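### The Cox model behind the reported risk ratio is not stated to share the site strata of the primary log-rank test, and the planned treatment-by-site test is unreliable at up to 19 degrees of freedom on about 70 events

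*Combined protocol and SAP*

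**What the plan says.** Site is the only factor that stratifies the randomisation (Sections 9.1.3 and 10.1). For the comparison of arms Section 10.8 follows it: "we will use a stratified log-rank statistic (using the stratification variables from the randomization procedure". The next sentence turns to modelling: "A Cox proportional hazards model with treatment and other important prognostic factors as covariates will be used for the multivariate analysis" of time to first ICD therapy, and risk ratios with 95% intervals come next. The prognostic factors are not listed, and site is neither named nor excluded. Section 10.1 adds region (US or Europe) to every model if the two populations differ at baseline, and plans a treatment-by-region interaction test.

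Section 10.8 expects no interaction between treatment and the stratification factors, but states that "formal tests for interactions will be assessed using proportional hazards models". It gives no pooling rule, minimum site size or random effect. On the number of sites, Section 7.1 says "The study will be conducted in up to 20 sites", and Section 8 caps each site at 90 patients. Sections 10.6 and 10.7 set 70 events from 462 patients. On the test level Section 10.8 says "The final analysis will be based on a two tailed 0.0492 level test".

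**The concern.** There are two linked points.

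- **Test and estimate.** The p-value conditions on site. The only model named for the effect on the primary endpoint is not said to do so, and its covariates are open. The analyst would settle the adjustment set behind the published ratio later, possibly with the data in view, and the ratio's interval could fall on the other side of significance from the primary test.
- **Interaction.** Because site is the only stratification factor, the planned test is treatment by site. With many sites and few events, some sites will have no event in one arm. Their treatment effects are then infinite, and the chi-squared reference for the likelihood-ratio test no longer holds. The risk is a false report that the treatment effect varies between sites.

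**Working it through.** **1. Events available.** Section 10.6 gives "18-months event rate in the ICD alone group of 19" per cent, 11.4% with RSDN, and 462 patients at 1:1. The plan's 70 is reproduced as an event yield: 462 × (0.19 + 0.114)/2 = 462 × 0.152 = 70.2 events at 18 months, before attrition. It is not reproduced as the requirement for "b) 85% power, (c) minimum follow-up of 18 months" with "two sided type I error fixed at 0.0492, assuming one interim analysis". The hazard ratio is ln 0.886 / ln 0.81 = 0.574 (log −0.554). Schoenfeld's formula gives 4 × (1.967 + 1.036)² / 0.554² = 36.07/0.307 = 117.5, so 118 events. That is a separate and larger issue. Seventy is used here because Section 10.8 censors at 18 months.

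**2. Test against estimate.** Simulated Cox hazard ratios, 20 equal sites, 400 trials per setting. The site log-hazard SDs are assumptions; the documents give none.

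| Site SD | Stratified | Unstratified |
|---|---|---|
| 0 | 0.583 | 0.582 |
| 0.5 | 0.558 | 0.565 |
| 1.0 | 0.577 | 0.604 |

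A further simulation used 18-month censoring, 5% attrition, unequal sites and 3,000 trials per setting. It compared a stratified test at |z| > 1.967 with an unstratified one at |z| > 1.96. They disagreed on significance in 2.6%, 3.4% and 5.8% of trials with 20 sites at SD 0, 0.5 and 0.8, and in 1.9%, 2.9% and 4.3% with 10 sites. Neither simulation includes prognostic covariates, so neither measures the planned multivariable model itself.

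**3. Sparsity by site.** Interaction degrees of freedom are sites minus 1, so at most 19. With S equal sites each arm of a site has m = 462/(2S) patients, and the chance of no event is 0.81^m (ICD alone) or 0.886^m (ICD + RSDN).

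| S | m | No event, ICD alone | No event, RSDN | Either arm | Expected such sites | No such site |
|---|---|---|---|---|---|---|
| 7 | 33.0 | 0.001 | 0.018 | 0.019 | 0.1 | 87% |
| 10 | 23.1 | 0.008 | 0.061 | 0.068 | 0.7 | 49% |
| 20 | 11.55 | 0.088 | 0.247 | 0.313 | 6.3 | 0.05% |

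For S = 20: 0.088 + 0.247 − 0.088 × 0.247 = 0.313; 20 × 0.313 = 6.3; (1 − 0.313)^20 = 0.0005. At 20 sites there are 70/20 = 3.5 events per site.

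**4. Behaviour of the test.** Likelihood-ratio rejection at nominal 5% with no true interaction, from two simulations:

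| Sites | Site-stratified baseline, 5% attrition, equal sites | Second simulation, equal sites | Second simulation, unequal sites |
|---|---|---|---|
| 7 | 6% | 10% | 8% |
| 10 | 10% | 9% | 12% |
| 20 | 11% | 17% | 16% |

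In the first simulation all site effects were finite in 86%, 44% and 0% of trials. The second used 300 trials per setting, so the standard error on 17% is √(0.17 × 0.83/300) = 2.2 points. The spread between the two is best read as a range.

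**5. More events.** With follow-up to the 36-month maximum and uniform accrual (an assumption), 462 patients without attrition give about 118 events. At 20 equal sites the chance that all site effects are finite rises only to about 15%.

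**6. The region alternative.** With 35 events per region (assumed split), the interaction standard error is √(4/35 + 4/35) = 0.48. For 80% power the ratio of hazard ratios must reach exp(2.80 × 0.478) = 3.8.

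**The case against.** The case against has real force.

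- A stratified log-rank test followed by a covariate-adjusted Cox model is common practice. Section 10.8 makes the log-rank the comparison and presents the Cox model as the multivariate analysis. A reader might infer that the plan leaves site out of the Cox model. The text does not say so: it is silent, and the unnamed prognostic factors could include site. What stands is that the plan does not tie the estimate to the test.
- A reader might infer that the treatment-by-site test cannot be fitted. The documents do not support that. Twenty is a ceiling; the 90-patient cap allows 462/90 = 5.1, so 6 sites; the Protocol Summary names seven plus others to be determined; and the record numbering in Section 11.1 runs to site 10. Even at 20 sites a statistic was returned. What stands is over-rejection.
- No decision in the plan depends on the interaction test, and the region test is already there. Both are true, and they limit the harm.
- The 95% interval does not match the 0.0492 test, but the multipliers are 1.960 and 1.967, a width difference of about 0.4%. That is cosmetic, and Section 10.8 gives 95% as its routine reporting level.

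**Conclusion.** The concern holds as a gap in specification and a poor choice of interaction test.

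Test and estimate are not tied to one model. The hazard ratio barely moves unless sites differ strongly, so a reader should not conclude that the published ratio is likely to contradict the primary result. In simulations without covariates the two disagreed on significance in about 2–6% of trials, with site SDs of 0 to 0.8 assumed.

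The interaction test is the more substantial half. At 20 equal sites about 6 have an arm without events, almost no trial has all site effects finite, and the false-positive rate is about 11–17% at nominal 5%. With 7–10 sites it is about 6–12%. These figures rest on the plan's 18-month rates and about 70 events; the number and sizes of sites are not fixed by the documents.

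**What to change.** In Section 10.8:

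- State that the primary hazard ratio comes from a Cox model with treatment, stratified by site to match the log-rank test.
- Keep the multivariable model as supportive, also stratified by site, and list its covariates in advance.
- Replace the fixed-effect treatment-by-site test with the one-degree-of-freedom treatment-by-region test of Section 10.1. Describe site variation with a random treatment-by-site effect, or after pooling small sites by a stated rule.

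In Section 10.1, note that each site lies in one region, so site strata absorb the region main effect. Only the treatment-by-region interaction can be fitted in these models, and the rule that adds region as a covariate to all models needs amending.

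The cost is SAP wording. Stratifying the model gives up about 1–3% of information, which the primary test already accepts. The region test has low power (step 6 of the working), so a non-significant result should not be read as showing equal effects in the two regions.

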9.2 POST-PROCEDURE

9.2.1 POST-PROCEDURE FOLLOW UP

- All patients will be monitored to verify vascular hemostasis prior to discharge from the hospital.
- All patients will receive either oral aspirin (81-325 mg QD) or clopidogrel (75 mg QD) or warfarin or one of the NOACs (dabigatran, rivaroxaban, Apixaban) for at least 1 week upon discharge.
- Medication and adverse event review will be performed prior to discharge.
- Complications including vascular, stroke, heart failure etc., and presence of ventricular arrhythmias will be documented.
- ICD programming: (see below section 9.2.3)
- The total number of episodes of VT, ATP, and Shocks will be documented at all visits.
- The follow-up includes:
 - 1 Month (\pm 14 days):
 - History and Physical
 - ICD interrogation
 - Office BP measurements (x2) including orthostatics
 - Review of Medications and Adverse events
 - 6 Months (\pm 30 days):
 - History and Physical
 - ICD interrogation
 - Office BP measurements (x2) including orthostatics
 - Lab tests (CBC, Electrolytes, BUN/Cr)
 - BNP Level

- Review of Medications and Adverse Events
 - Repeat Renal Ultrasound or MR/CT Angiography
- 12 Months (\pm 30 days):
 - History and Physical
 - ICD interrogation
 - EKG
 - Office BP measurements (x2) including orthostatics
 - Lab tests (CBC, Electrolytes, BUN/Cr)
 - Blood for Renal Hormones (OPTIONAL)
 - BNP Level
 - Review of Medications and Adverse Events
 - Repeat TTE
- 18 Months (\pm 30 days):
 - History and Physical
 - ICD interrogation
 - Office BP measurements (x2) including orthostatics
 - Review of Medications and Adverse Events
- 24 Months (\pm 30 days):
 - History and Physical
 - ICD interrogation
 - Office BP measurements (x2) including orthostatics
 - Lab tests (CBC, Electrolytes, BUN/Cr)
 - BNP Level
 - Review of Medications and Adverse Events
- 36 Months (\pm 30 days):
 - History and Physical
 - ICD interrogation
 - Office BP measurements (x2) including orthostatics
 - Lab tests (CBC, Electrolytes, BUN/Cr)
 - BNP Level
 - Review of Medications and Adverse Events

Patients will be followed for a maximum of 36 months until the final patient reaches the 18 month follow-up time point. Once the final patient reaches the 18 month follow-up time point, all follow-ups will cease.

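### Section 10.8 can be read as censoring at month 18 although follow-up runs to month 36; the censoring date and the 70-event trigger must be settled together

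*Combined protocol and SAP*

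**What the plan says.** The primary endpoint (sections 5.1 and 10.3) is time to first ICD therapy or incessant VT, with no fixed horizon. Section 10.8 measures survival time from randomization to the first therapy, then treats patients as "censored if they are alive and free of ICD events at the end of the 18-month follow-up period".

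Other sections describe the follow-up differently:

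- Section 10.6 sizes the trial with "minimum follow-up of 18 months" and an "accrual period of 48 months and non-uniform accrual".
- Section 9.2.1 states: "Patients will be followed for a maximum of 36 months until the final patient reaches the 18 month follow-up time point". All follow-up then stops.
- Table 1 and section 9.2.1 schedule ICD interrogation at 1, 6, 12, 18, 24 and 36 months and record VT, ATP and shock counts at every visit.
- Section 9.3.2 has a committee adjudicate all ICD events, and section 10.9 analyses safety over the whole of follow-up.
- The Design row of the Protocol Summary gives a third figure, a 12-month follow-up period.

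Section 10.7 places the interim and final analyses at about 35 and 70 events.

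**The concern.** On the literal reading, a minimum has become a maximum. A patient whose first therapy is found at month 20 or 30 would enter the log-rank test and Cox model as event-free at month 18, although the event was recorded and adjudicated. No section explains why efficacy alone would be truncated. At stake are the power of the primary test and the width of the hazard-ratio interval, from data the trial collects anyway. A programmer following section 10.8 as written could well apply the cut.

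**Working it through.** **Inputs.** Section 10.6 gives 19% vs 11.4% at 18 months, two-sided alpha 0.0492, 85% power, 48-month accrual of unstated shape, 70 events and 462 patients. The Protocol Summary gives 231 per arm. Section 10.7 gives the critical value 1.967. Section 9.2.1 gives a 36-month maximum and a common close when the last patient reaches month 18, so about trial month 48 + 18 = 66.

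**Assumptions not in the documents.** Constant hazards, the same hazard ratio after month 18, four accrual shapes, and no attrition unless stated.

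**Hazards.** Control: −ln(0.81)/18 = 0.01171 per month. RSDN: −ln(0.886)/18 = 0.00672 per month. HR = 0.574 and |ln HR| = 0.554.

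**The plan's own figure.** If every patient stops at exactly month 18, expected events are 231 × (0.19 + 0.114) = 70.2. That matches the stated 70. The events needed for 85% power (Schoenfeld) are 4 × (1.967 + 1.036)² / 0.554² ≈ 117.4, so 118. The 70 therefore fits an 18-month cap but not 85% power. Comparing two proportions at 18 months needs about 804 patients. The exponential sample-size formula with all follow-up and uniform accrual needs about 479, close to 462. So the 462/85% pair fits longer follow-up, and the 70 fits the cap.

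**Capped against all follow-up.** Each patient's follow-up is min(cap, 66 − entry month), so late entrants get between 18 and 36 months. Events = 231 × mean[1 − exp(−h × follow-up)], summed over arms. Power = Φ(√events × 0.554/2 − 1.967).

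| Analysis | Events | Power | Events discarded by cap | Points lost to cap |
|---|---|---|---|---|
| Cap at month 18 | 70.2 | 63.9% | – | – |
| All, quadratic back-loaded accrual | 104.1 | 80.6% | 33% | 17 |
| All, linear back-loaded | 110.3 | 82.8% | 36% | 19 |
| All, uniform | 118.4 | 85.3% | 41% | 21 |
| All, linear front-loaded | 126.5 | 87.5% | 44% | 24 |

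Under uniform accrual the standard error of the log hazard ratio is √(70.2/118.4) = 0.77 of its capped value. Log-rank simulation (6,000 trials per shape) gave 61–63% capped and 79–87% on all follow-up.

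**Sensitivity.**

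- Cubic back-loaded accrual: 99.3 events, 78.7% power; the cap discards 29% and costs 15 points.
- 5% attrition per 18 months, uniform accrual: 68.5 vs 113.2 events, 62.8% vs 83.7% power.
- Both hazards halve after month 18: 18–30% of events discarded, 8–15 points lost (cubic accrual included).
- Both hazards fall to a quarter after month 18: 10–18% and 4–8 points.
- Effect fades after month 18 (simulation; capped power about 62–64%): all-follow-up power is about 70–72% at a late HR of 0.7, about 60–62% at 0.8, and about 50% or less at 0.9 and above.

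**The 70-event trigger.** If later events count but section 10.7 is unchanged, the 70th event is expected at about month 34 (front-loaded), 43 (uniform), 51 (linear back-loaded) or 55 (quadratic). Power at 70 events is still about 64%. Under uniform accrual, month 43 falls before the 48-month accrual ends.

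**The case against.** The phrase in section 10.8 may mean the common close, when the last patient reaches month 18. That reading fits the minimum follow-up in section 10.6 and a survival time with no horizon, and on it no events are lost. This stands: the documents do not establish the cap. Against it, an 18-month period most naturally describes one patient's duration, and the 70-event count is what such a cap would yield. On either reading the sentence needs rewriting.

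A reader might also infer that the censoring sentence causes the power shortfall and that rewording it restores 85%. The documents do not support that. The 64% is the power of 70 events however they are reached, and section 10.7 runs the final analysis at 70. Counting later events under that trigger only brings the analysis forward.

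Nor is a fixed 18-month horizon wrong in itself. Section 10.6 states its rate and its reduction at 18 months, and a truncated test does better if the effect largely fades. The plan gives no event rate or effect after month 18, and section 10.8 includes a proportional-hazards test. The inconsistency with the follow-up schedule and the stated 85% remains.

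**Conclusion.** The point holds in conditional form. Section 10.8 does not settle whether event-free patients are censored at their own month 18 or at the common close, and the literal reading conflicts with sections 5.1, 9.2.1, 10.3 and 10.6. If it is a per-patient cap, the trial analyses about 70 events with about 64% power. Against all follow-up, that discards about 33–44% of events (41% under uniform accrual) and costs about 17–24 points.

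These sizes are not properties of the plan alone. They rest on constant hazards, an unchanged hazard ratio after month 18 and an assumed accrual shape. They shrink if event rates fall later, and the advantage of longer follow-up is gone at a late hazard ratio of about 0.8 or higher. Under either reading, 70 events do not give 85% power at the planned effect.

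**What to change.** **Section 10.8.** Censor patients without a primary event at the last ICD interrogation up to month 36 or the common study close, whichever comes first. State how deaths without a primary event are handled; the present sentence covers only patients who are alive. Base the stratified log-rank test and Cox model on that follow-up. Keep the 18-month Kaplan-Meier contrast and an analysis truncated at month 18 as supportive.

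**Sections 10.6 and 10.7.** Replace the 70-event trigger in one of two ways:

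- Set the target to about 118 events (Schoenfeld, HR 0.574), with the interim look at half, about 59. Under back-loaded accrual only about 104–110 events are expected by the common close, so say what happens if the target is not reached.
- Run the final analysis at the common close and state the power for the expected events.

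Give the assumed accrual pattern in either case.

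**If an 18-month cap is intended,** say so and restate the power of 462 patients as about 64%.

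**Protocol Summary.** Reconcile the 12-month follow-up period with section 9.2.1.

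**Cost.** Wording and event targets only, with no new patients, visits or data; it should be done before unblinding. The final analysis would come later than the 70th event. The hazard ratio would average over up to 36 months and be diluted if the effect fades, which the supportive 18-month analysis would show.

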Design:	This study is a prospective, multicenter, single-blinded, randomized (1:1) control trial evaluating the effectiveness of RSDN in the primary prevention of ICD therapy in patients with ischemic or non-ischemic ventricular dysfunction who are to receive an ICD for either i) secondary prevention, or ii) primary prevention + inducible VT by programmed ventricular stimulation at the time of ICD implantation. These patients will be randomized to ICD alone or ICD + RSDN. Subjects will only be eligible for this study if they are \geq 18 years of age and have a history of structural heart disease (post-MI, dilated cardiomyopathy, sarcoid myopathy, hypertrophic cardiomyopathy, etc.), and are planned for ICD implantation for: i. Secondary prevention (e.g.: VT/VF arrest, sustained VT, syncope/inducible VT) ii. Primary prevention + inducible MMVT during induction via ICD lead testing. In addition, eligible patients will have accessible renal vasculature (as determined by renal angiography).
	The patient will be blinded to the results of randomization. Once randomized, study group subjects will undergo a strategy of catheter-based renal sympathetic denervation + ICD implantation (if not already present). Control patients will receive standard ICD implantation alone (if not already present). Follow-up will be conducted in regular intervals over a 12-month period.
Enrollment:	Total: 462 subjects (231 control group, 231 study group)
	An interim safety analysis will be performed after the first 50 subjects (25 control group, 25 study group) have completed their 6-month follow-up visit.
Clinical Sites:	
• Icahn School of Medicine at Mount Sinai• Homolka Hospital, Prague, Czech Republic• Heart Center U SV. Anny Hospital, Brno, Czech Republic• Massachusetts General Hospital• Regional Cardiology, Sacramento, California• Medical University of South Carolina• Florida Hospital, Orlando, Florida

	
 • Other Sites TBD
Time Course:	Enrollment: Over 4 years

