In an initial pilot study, an irrigated radiofrequency catheter (Celsius Thermocool F-Curve RF catheter, Biosense-Webster, Inc., Diamond Bar, California) was used in 20 patients with ischemic or non-ischemic ventricular dysfunction, who were scheduled to receive an ICD for either i) secondary prevention, or ii) primary prevention + inducible VT by programmed ventricular stimulation at the time of ICD implantation ([name], unpublished observation). Although we have favorable single-operator, single-center safety data in another RSDN trial, preliminary review of the six-month renal ultrasound data provided a higher than expected event rate of renal artery stenosis. As such, the protocol has been amended to allow for the use of a dedicated renal sympathetic denervation catheter system: the Vessix™ Renal Denervation System (Boston Scientific, Quincy, Massachusetts).

4. SCHEDULE OF TREATMENT AND TESTS:

TABLE 1:

	Baseline	Procedure*	Discharge	1, 6,12,18,24,36 months**
Type of visit	Office	Hospital		Office
Informed Consent	X			
Brief History & Physical	X			X
Blood Laboratory Testing: CBC, Electrolytes, BUN/ Creatinine, BNP	X			X (6, 12, 24, 36m)
Blood for Renal Hormones (OPTIONAL*)	X			X (12m)
TTE	X			X (12 m)
Renal Angiography		X		
Ultrasound or MR/ CT Angiography				X (6 m)
Randomization		X		
Renal Sympathetic Denervation		X		
ICD Interrogation	X			X
EKG	X			X (12m)
Office BP Measurements (including orthostatic BPs)	X			X
Medications	X		X	X
Adverse Events		X	X	X

* Hormonal measurements are optional in cases where the cost would be prohibitively burdensome to patients or hospital/clinic facilities are not available to allow for their measurement.

** - Visit windows – 1 Month (\pm 14 days); 6, 12, 18, 24, 36 Months (\pm 30 days)

5. ENDPOINTS:

5.1 PRIMARY ENDPOINT:

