The primary safety objective is to demonstrate that the incidence of serious adverse events (events that cause clinically relevant changes in patient's health, or any event that is life-threatening, results in a fatality, results in permanent disability, requires hospitalization, or prolongs an existing hospital stay) is not increased with the use of the ICD + RSDN compared to ICD alone.

10.5 SECONDARY ENDPOINTS:

The following secondary endpoints will be assessed:

- Appropriate ICD therapy assessed in the full intention-to-treat patient cohort
- Inappropriate ICD therapy
- Number of Hospitalizations for Cardiovascular Causes.
- Total VT burden (Number of episodes).
- All-Cause Mortality.
- The occurrence of ICD storm, defined as ≥ 3 appropriate shock therapies within 24 hours.
- Differences in BUN/creatinine measurements.
- Procedure related adverse events including, but not limited to hematomas, pseudoaneurysms and renal artery stenosis.
- Development of orthostatic hypotension
- 30-day Major Complication Rate defined as death, stroke, MI or any other serious adverse events related to the treatment or procedure within the first 30 days or through hospital discharge (whichever is longer).

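### Section 10.8 sends all binary and count secondary endpoints to repeated-measures GEE, which does not suit mortality, event-occurrence endpoints or event counts when planned follow-up runs from 18 to 36 months

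*Combined protocol and SAP*

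**What the plan says.** Section 10.8, under the analysis of secondary endpoints, has two rules. Continuous variables go to mixed-effects models. For the rest: "For binary and discrete outcomes we will use generalized estimating equations (GEE"), used "to fit logistic or log-linear models that account for the dependency of the repeated measures".

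Section 10.5 lists the endpoints that this second rule must cover. They include appropriate ICD therapy, inappropriate ICD therapy, all-cause mortality, occurrence of ICD storm, the number of cardiovascular hospitalizations, and "Total VT burden (Number of episodes"). None of these has a time frame or a method of its own.

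On follow-up, Section 9.2.1 says: "Patients will be followed for a maximum of 36 months until the final patient reaches the 18 month follow-up time point". Section 10.6 assumes "minimum follow-up of 18 months" and "accrual period of 48 months and non-uniform accrual". Table 1 in Section 4 sets visits at "1, 6,12,18,24,36 months". The design row of the Protocol Summary differs: "Follow-up will be conducted in regular intervals over a 12-month period".

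Other tools are named elsewhere, but for other endpoints. Kaplan-Meier curves, the stratified log-rank test, Cox regression and censoring at 18 months are written for the primary endpoint (10.8). An incidence rate ratio from Poisson regression is written for serious adverse events (10.9).

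**The concern.** A repeated-measures model needs an outcome that is measured again at each occasion. Death does not fit that. Whether a patient has had a therapy or a storm depends on how long the patient was watched, and when the event occurred carries information that a logistic model of occurrence discards. Episode and hospitalization counts accumulate with time at risk, so comparing them without person-time mixes the event rate with survival: an arm that lives longer has more time to accrue events.

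At stake are the secondary efficacy results, mortality and appropriate therapy among them. They could be reported as odds ratios with no stated time frame and count ratios that partly reflect survival. The plan also leaves the analyst to choose, with data in hand, what the repeated unit is and over what window.

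**Working it through.** No stated figure is in dispute. The check is how far follow-up varies and what follows if it is ignored.

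**1. Spread of planned follow-up.** Accrual is 48 months and the last patient is followed for 18, so the study ends at month 66. A patient entering at month e has planned follow-up min(36, 66 − e). All who enter by month 30 reach 36 months. Under uniform accrual (an assumption; the plan says non-uniform and gives no shape) that is 30/48 = 62.5%, with mean 0.625 × 36 + 0.375 × 27 = 32.6 months. A ramp-up shape gives 39% reaching 36 months and a front-loaded shape 86%, with means of about 30 and 35 months.

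**2. Why a time frame is needed.** Take the plan's figures for the primary composite (Section 10.6: 19% vs 11.4% at 18 months) as a stand-in, with constant hazards.
- Hazard ratio: ln(0.886)/ln(0.81) = 0.574, the same at every horizon.
- Control risk: 19.0% at 18 months; 1 − 0.81² = 34.4% at 36 months.
- RSDN risk: 11.4% at 18 months; 1 − 0.886² = 21.5% at 36 months.
- Odds ratio: 0.549 at 18 months, 0.523 at 36 months.

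An odds ratio over mixed follow-up belongs to neither horizon. This is a problem of definition, not a difference between arms.

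**3. Size of the count bias if mortality differs.** For yearly mortality q, let m = −ln(1 − q). Mean years alive within T years are (1 − (1 − q)^T)/m. With equal event rates and no offset, the count ratio equals the exposure ratio. All mortality rates are assumed.

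| Yearly mortality | T (years) | Exposure, higher-mortality arm | Exposure, lower-mortality arm | Ratio |
|---|---|---|---|---|
| 10% vs 8% | 1.5 | 1.388 | 1.410 | 1.016 |
| 10% vs 8% | 3 | 2.572 | 2.654 | 1.032 |
| 12% vs 6% | 1.5 | 1.365 | 1.432 | 1.049 |
| 12% vs 6% | 3 | 2.492 | 2.738 | 1.099 |

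**4. Effect on tests.** Simulation: 231 per arm, 6,000 runs, uniform accrual, follow-up as in step 1, control event hazard from the 19% figure. Assumed inputs are yearly mortality (control vs RSDN), 0.06 counts per month and dispersion 1.5. It takes the simplest reading of the rule: one yes/no outcome and one count per patient. Percentages are two-sided 5% rejection rates; the simulation error on a true 5% is √(0.05 × 0.95/6000) = 0.3 points.

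| Scenario | Yes/no odds ratio | Log-rank | Count ratio, no offset | Count ratio, offset |
|---|---|---|---|---|
| No effect, 7% vs 7% | 1.00; 4.7% | 4.7% | 1.00; 6.0% | 1.00; 5.8% |
| No effect, 10% vs 5% | 1.10; 6.8% | 4.8% | 1.07; 8.5% | 1.00; 5.6% |
| No effect, 15% vs 7.5% | 1.15; 10.2% | 5.3% | 1.12; 12.2% | 1.00; 5.5% |
| HR 0.574, count ratio 0.60; 7% vs 7% | 0.54; 79% | 81% | 0.60; 94% | 0.60; 94% |
| HR 0.574, count ratio 0.60; 15% vs 7.5% | 0.62; 56% | 79% | 0.67; 76% | 0.60; 94% |

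With equal mortality the methods barely differ. The distortion appears, and grows, only as mortality separates.

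**The case against.** The strongest reply is that the sentence in 10.8 is generic, and more may be read into it than it says.

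- **Withdrawn or short-follow-up patients.** A reader might infer that they are counted as event-free alongside patients followed for 36 months. The plan does not say so. Its missing-data text uses all information up to withdrawal, and in a visit-level GEE a patient simply stops contributing. What stands is that the repeated unit is undefined, visit intervals run from 1 to 12 months, and death does not repeat under any unit. That text also sends other variables to likelihood-based methods, which GEE is not, and it does not mention death.
- **Offset.** The plan neither includes nor excludes one. The gap is that person-time is not addressed for counts, not that a wrong model is written down.
- **Follow-up length.** A reader might take the higher risk at 36 than at 18 months as a treatment bias. It is not: 1:1 randomization in blocks, stratified by site, balances planned follow-up, and the equal-mortality rows above show no bias.
- **Recurrence.** Therapies and storms can recur, so only death is certainly a once-only event. Section 10.5 does not say whether the first event is meant; for storm it says occurrence.
- **Overlap.** The primary analysis already treats first therapy of either kind as time to event, and deaths and hospitalizations enter the serious-adverse-event rate ratio. Both pool events and do not replace the separate secondary analyses.
- **Shorter follow-up elsewhere.** The 12-month statement in the Protocol Summary and the 18-month censoring in 10.8 could suggest a common window. The first conflicts with 9.2.1; the second is written for the primary endpoint only.

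**Conclusion.** The point holds as a mismatch between the stated method and several secondary endpoints. It is certain for all-cause mortality. It is well supported for the occurrence of appropriate therapy, inappropriate therapy and storm, and for the two count endpoints, because planned follow-up varies and no time frame or person-time is given.

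The consequence is an effect measure with no defined time frame in every case. Power loss is about 2 points with equal mortality in the simulation and larger only where mortality differs. Bias needs death or withdrawal to differ by arm: 1.6-3.2% in the count ratio at 10% vs 8% yearly mortality, 4.9-9.9% at 12% vs 6%, against the better-surviving arm. Those mortality rates are assumptions. The documents give none and offer no basis for expecting mortality to be halved, so the larger figures mark a range and are not a forecast.

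The documents do not support a claim that the trial's main result is at risk. The primary analysis has its own time-to-event method. Orthostatic hypotension, which can be measured at each visit, and the 30-day complication rate, with its short early window, are also unaffected.

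**What to change.** Replace the single GEE rule in 10.8 with methods by endpoint type:

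- **All-cause mortality:** site-stratified log-rank test and Cox model.
- **First appropriate therapy, first inappropriate therapy, first storm:** time to first event from randomization, with death handled as a competing event. For example, use cumulative incidence curves and cause-specific hazard ratios.
- **VT episodes and cardiovascular hospitalizations:** an overdispersed count model such as negative binomial with a log(follow-up time) offset, follow-up ending at death, withdrawal or study end. An equivalent recurrent-event model would also serve.
- **Visit-level repeated measures:** keep GEE and mixed models.

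State the follow-up window for each endpoint, and reconcile the 12-month wording in the Protocol Summary and the 18-month period in 10.8 with Section 9.2.1.

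The cost is SAP wording and slightly more analysis work. ICD interrogations and adverse events are already collected at the scheduled visits, so no new visits or patients are needed.
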